# **1.3. Preclinical Experience**

Not applicable.

# 2. Study Hypotheses/Objectives

### 2.1. Hypotheses

### Clinical hypothesis and research question

The research question we will address: Is there a benefit to allowing children with high threshold peanut allergy to ingest home measured amounts of peanut below their threshold, as compared to standard care avoidance?

We hypothesize that for persons with high threshold peanut allergy, ingesting sub-threshold amounts of the allergen (amounts not causing symptoms) will result in an ability to ingest higher amounts with time (desensitization) and potentially sustained unresponsiveness (SU).

We also hypothesize that the approach will be safe and improve quality of life compared to avoidance.

We base these hypotheses in part on observations from studies of OIT in low threshold subjects as described in 1.2 above.

### Mechanistic hypothesis

We hypothesize that ingestion of sub-threshold amounts of peanut protein will be associated with peanut-specific immunomodulation, consistent with the development of desensitization and sustained unresponsiveness. Specifically, we hypothesize that ingestion of peanut will be associated with changes in peanut-specific humoral immunity, with a decrease in anaphylaxis-promoting IgE antibodies and an increase in blocking antibodies, and a modulation of the peanut-specific T cell response consistent with immune tolerance. We anticipate that individuals' potential for desensitization via the ingestion of subthreshold amounts of peanut protein will be detectable as early IgE and IgG4 epitope-specific and transcriptional signatures in peripheral blood, and that data-driven selection of these signatures will yield a clinically useful biomarker of desensitization potential. Further, these transcriptional signatures will elucidate functional pathways underlying desensitization success.

### 2.2. Primary Objective(s)

### Primary clinical objective

The primary objective of this study is to determine whether allowing ingestion of sub-threshold amounts of peanut in subjects with a high threshold (those who tolerate at least 143 mg peanut protein on supervised double-blind, placebocontrolled oral food challenge [DBPCFC]) will be associated with attaining even higher thresholds over time compared to those avoiding peanut. Primary mechanistic objectives

The primary mechanistic objectives are to elucidate immune mechanisms induced by daily ingestion of sub-threshold amounts of peanut, and to identify biomarkers of and functional pathways underlying desensitization potential. We will test if peanut ingestion is associated with the following immune and transcriptomic processes:

- Suppression of serum peanut-specific IgE
- Increase in serum peanut-specific IgG and IgG4
- Change in peanut IgE and IgG4 epitope binding scores
- Decrease in basophil activation tests
- Decrease in peanut-specific multifunctional Th2 cells
- Increase in peanut-specific regulatory T cells
- Change in peripheral blood transcriptional signatures
- Up and downregulation of distinct gene ontology pathways

### 2.3. Secondary Objective(s)

### Secondary clinical objectives

The secondary clinical objectives of this study are to determine whether ingesting sub-threshold amounts of peanut in children with high threshold peanut allergy, compared to avoidance, will:

- A) Result in increased rates of sustained unresponsiveness.
- B) Have positive effects on quality of life.
- C) Be a safe approach.

# Secondary mechanistic objectives

Secondary mechanistic objectives are to:

- A) Determine if immune and transcriptomic measures obtained early in the course of ingestion exposure can predict development of desensitization or sustained unresponsiveness.
- B) Identify immune and genomic biomarkers of the high threshold phenotype.
- C) Identify early-appearing functional pathways underlying a successful desensitization course (exploratory).

# 3. Study Design

# **3.1.** Description of Study Design

This is a prospective, two-arm parallel-group, randomized (1:1; 36 per group), controlled, open label trial of peanut ingestion and dose escalation (versus avoidance) in children age 4 to less than 15 years at enrollment who have high threshold peanut allergy (tolerate  $\geq$ 143 mg but not 5043 mg cumulative peanut protein) based on DBPCFC. It is anticipated that approximately 150-200 subjects undergoing DBPCFCs will be needed to identify 72 participants for randomization.

### 3.1.1 Screening DBPCFC to determine threshold and identify subjects for randomization

Subject fulfilling inclusion/exclusion criteria will undergo an initial DBPCFC according to modified PRACTALL guidelines. Dosing is 3 mg, 10 mg, 30 mg, 100 mg, 300 mg, 600 mg, 1000 mg, 3000 mg, 4000 mg peanut protein. The dosing interval is 20-30 minutes except the final dose, 4000 mg, will be given 60 minutes after the 3000 mg dose. This baseline DBPCFC will phenotype participants as having LT peanut allergy, HT peanut allergy or no peanut allergy (Figure 1). Blood samples will be obtained in association with screening DBPCFC for mechanistic studies associated with peanut allergy endotypes. Those tolerating 9043 mg (approximately 8 teaspoons of peanut butter or equivalent) will be permitted to add peanut to the diet.

Figure 1. Initial screening DBPCFC to phenotype threshold, obtain biosamples, and identify those qualified for randomization.

# 3.1.2. Overview of trial scheme

Children with HT peanut allergy will be randomized to continue avoidance (control) or to ingest a home measured amount of peanut daily (intervention) based on their threshold. Subjects in the intervention group return to the research unit for re-challenge to increased amounts of peanut at 8 week intervals and are instructed to ingest the larger amount if tolerated. A repeat DBPCFC will be performed 8 weeks after reaching 1 tablespoon (or equivalent) in the intervention group, or at 72 weeks. A repeat DBPCFC will be performed in the control group at a time calculated according to a surveillance algorithm to ensure similar lengths between initial and desensitization DPBCFC between the two groups (see Section 13.3). Subjects in the intervention arm tolerating the full challenge amount will add peanut to the diet for 16 weeks and then avoid peanut for 8 weeks, followed by a DBPCFC to assess for sustained unresponsiveness [SU] (ability to consume without reaction after a period of avoidance). The study scheme is shown in Figure 2.

### Figure 2. Randomized Intervention Study scheme

### **3.1.3 Intervention Arm Procedures**

Children randomized to the active arm will return for an observed administration of the highest amount of peanut they should tolerate with no or minimal (oral) symptoms based on their baseline DBPCFC. The starting amount of peanut butter will be 1/8th teaspoon [approximately 140 mg peanut protein] if they reacted at 443 mg cumulative dose on DBPCFC, ¼ teaspoon [approximately 280 mg peanut protein], if they reacted at 1043 mg cumulative dose on DBPCFC, 3/8 teaspoon [approximately 430 mg peanut protein] for a reaction at 2043 mg cumulative dose) or 1 teaspoon [approximately 1140 mg] for a reaction at 5043 mg cumulative dose. To continue on daily peanut, the 1/8th teaspoon supervised feeding post food challenge must be tolerated. Study participants/families will be given detailed instructions

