### AADCRC

specifying the types and amounts of the commercial foods allowed for home ingestion. They also will be required to strictly avoid the food allergen other than the amount under the study. They will return every 8 weeks to attempt a supervised feeding of the next higher amount, as shown in **Figure 2**. If successfully consumed, they will continue the one step higher amount daily. When participants have exceeded 3/8 teaspoon of peanut butter, alternative forms (Bamba™, candies) can be substituted but such substitutions will be performed as observed feedings. (Table available in the MOP.) If subjects have symptoms at 1/8 teaspoon peanut butter during the study, they will be permitted to trial 1/16th teaspoon under observed feeding, but this will be the lowest amount allowed in the study.

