### Visit 1. Initial feeding challenge with subthreshold amount of peanut (visit length 2-3 hours)

- Physical exam, vital signs, medical history
- Spirometry (or peak flow under age 7, or if spirometry not allowed per COVID protocols)
- Open oral food challenge to amount determined by DBPCFC (Section 3.1.3) to confirm tolerance of threshold (if failed, can return for repeated Visit 1 with next lower dose if not already at 1/8 teaspoon).
- Training on measuring amounts for home use
- Provision of diaries and contact instructions

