### 8.4 Unscheduled Visits

If disease activity increases or other concerns arise between regularly scheduled visits, participants will be instructed to contact study personnel and may be asked to return to the study site for an "unscheduled" visit. If the participant becomes/is unable to ingest at least 1/8 teaspoon of peanut butter, they will undergo a supervised feeding of 1/16th teaspoon, which is the lowest amount permitted and may become the daily amount if tolerated. If the participant cannot ingest 1/16th teaspoon of peanut butter they will be considered a treatment failure and will stop any daily ingestion, but will undergo the endpoint DBPCFCs at 72 weeks.

The following circumstances may lead to unscheduled visits (active arm):

1. Concern regarding peanut ingestion triggering increased chronic symptoms (e.g., increased eczema, gastrointestinal symptoms).

Procedures (1-8 hour visit):

- Physical exam, vital signs, medical history
- Spirometry (or peak flow under age 7, or if spirometry not allowed per COVID protocols)
- DBPCFC to the amount being ingested on a daily basis, or supervised open feeding of the amount ingested on a daily basis, or supervised feeding of a lower amount, as deemed necessary for full evaluation

The PI/Investigator and family will determine whether to continue daily ingestion, reduce the daily amount, or follow off intervention, and/or refer for additional medical evaluation (i.e., endoscopy).

2. Concern regarding acute symptoms from home ingestion.

Participants will be instructed to contact the PI/Investigator/study team for acute allergic symptoms (with the exception of oral pruritus, mild transient abdominal discomfort, or perioral redness/hives). The investigator will determine the best course of action, with possible actions being the following:

- 1. Continue with daily home dosing
- 2. Return for an observed ingestion of the same amount
- 3. Return for an observed ingestion of a step lower amount.
- 4. Discontinuation of ingestion

The following process algorithm will be applied regarding symptoms associated with the daily ingestion.

If the subject only experiences oral/pharyngeal pruritus, or perioral redness/hives, or mild transient abdominal discomfort, the daily ingestion may continue. Instructions about eating peanut with meals will be reviewed. If the symptoms are bothersome or persistent, procedures per #1 above (chronic symptoms) will be followed.

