If the subject experiences *mild symptoms*, defined as:

- Skin non-perioral hives/swelling, skin flushing or pruritus
- Respiratory rhinorrhea/sneezing, nasal congestion, occasional cough, throat discomfort
- GI abdominal pain that is more than mild transient/minor episode of vomit

The action should be either to repeat the daily amount at home, or a reduced amount, or to have the subject return to the site for a repeat of the ingested amount or to trial a step lower amount (at the physician's discretion). If the amount is tolerated, then the subject will continue on that amount until the next scheduled visit. If the ingestion again causes mild symptoms, then the subject may return to the site to trial a lower amount, as possible.

If the subject experiences *moderate symptoms*, defined as:

- Skin systemic hives/swelling
- o Respiratory throat tightness without hoarseness, persistent cough, wheezing without dyspnea
- GI persistent moderate abdominal pain/cramping/nausea, increased vomiting

The action should be to have the subject return to trial a lower amount, as possible and with physician discretion. If this amount is tolerated, it will be continued as the daily home ingestion amount until the next scheduled visit. If the amount is not tolerated, then a discussion with the Study PI or Co-PI will ensue to make a decision about whether to continue the subject on active ingestion in the study.

If the subject experiences *severe symptoms*, defined as:

- Respiratory laryngeal edema, throat tightness with hoarseness, wheezing with dyspnea
- GI significant severe abdominal pain/cramping/repetitive vomiting
- Neurological change in mental status
- Circulatory hypotension

The action should be to treat the subject, and at the physician's discretion either 1) have them return to the site for trial of a 2 step lower (at least) amount under observation or 2) discontinue them from the active arm. If the subject tolerates the reduction, then they will remain on that amount until the next scheduled visit. A discussion with the Study PI or Co-PI may ensue to make a decision about whether to continue the subject on active treatment in the study.

For a completed ingestion visit with no symptoms, subjects should be observed for 30 minutes. For mild symptoms, subjects should have a 1-2 hours post ingestion observation period. For moderate to severe

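### The protocol gives two incompatible rules for a child who does not tolerate 1/8 teaspoon at the first supervised feeding

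*Protocol*

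**What the plan says.** Four statements in the protocol bear on a child who cannot take 1/8 teaspoon.

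- **3.1.3, starting amount and entry condition.** The lowest stratum starts at 1/8 "teaspoon [approximately 140 mg peanut protein] if they reacted at 443 mg cumulative dose on DBPCFC". For daily peanut to continue, the 1/8 "teaspoon supervised feeding post food challenge must be tolerated".
- **8.3, Visit 1.** The open feeding may be repeated at a smaller amount, with a limit: "if failed, can return for repeated Visit 1 with next lower dose if not already at 1/8 teaspoon".
- **3.1.3, closing sentence.** "If subjects have symptoms at 1/8 teaspoon peanut butter during the study, they will be permitted to trial" 1/16 teaspoon under observation, as the lowest amount in the study.
- **8.4, opening paragraph.** "If the participant becomes/is unable to ingest at least 1/8 teaspoon of peanut butter, they will undergo a supervised feeding of" 1/16 teaspoon, "which is the lowest amount permitted and may become the daily amount if tolerated". If the child cannot take 1/16 "teaspoon of peanut butter they will be considered a treatment failure and will stop any daily ingestion", with the endpoint challenge at 72 weeks.

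For severe symptoms, 8.4 separately gives the physician two choices: to "have them return to the site for trial of a 2 step lower (at least) amount under observation", or to discontinue the child from the active arm.

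SAP 6.3 counts a child assigned to ingestion who permanently stops peanut as a crossover. SAP 4 requires attendance at two-thirds of the updosing visits, and at the desensitization challenge, for intervention-arm membership of the per-protocol population.

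**The concern.** A child who fails 1/8 teaspoon at Visit 1 does not meet the entry condition and has no lower repeat. Under 8.4 the same child is to be fed 1/16 teaspoon and may stay on it. One rule ends the intervention before it starts and the other can keep it going.

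At stake is whether a randomized child gets any of the assigned treatment, and how that child is then counted. These are the children closest to their threshold, and the instructions concern continuing an allergen after a failed supervised feeding. If similar children are handled differently, exposure and discontinuation in this group depend on which section is applied.

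**Working it through.** **Step 1: who can meet the conflict.** A 443 mg child starts at 1/8 teaspoon and meets it on failing Visit 1. A child from a higher stratum who fails a larger amount may repeat Visit 1 lower, and meets it on failing at 1/8 teaspoon. So it is not confined to the lowest stratum, and within that stratum it reaches only those who fail.

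**Step 2: the rules side by side.**

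| Situation | 3.1.3 entry condition and 8.3 Visit 1 | 3.1.3 closing sentence and 8.4 opening | Compatible? |
|---|---|---|---|
| Fails 1/8 tsp at a first or repeated Visit 1 | Condition for daily peanut not met; no lower repeat | 1/16 tsp permitted (3.1.3) or required (8.4); may become the daily amount | No |
| Tolerated 1/8 tsp, later loses tolerance, symptoms not severe | Condition already met; nothing further said | 1/16 tsp available | Yes |
| Severe symptoms at 1/8 tsp in later home use | Nothing further said | 1/16 tsp, with no severity limit | Unclear against the severe-symptom rule in 8.4 |

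There are two rules across three sections: 3.1.3 conflicts with itself, and 8.3 conflicts with 8.4.

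**Step 3: the severe-symptom row.** Below 1/8 teaspoon the only amount is 1/16 teaspoon, one step down. A reduction of two or more steps does not exist there, so the severe-symptom rule leaves only discontinuation. The text does not say whether that rule overrides the 1/16 teaspoon provision.

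**Step 4: how the child is counted.**

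- ITT (SAP 4): included either way, in the assigned group.
- Safety population (SAP 4): included either way, because the Visit 1 feeding is itself peanut after the baseline challenge.
- Crossover (SAP 6.3): yes if taken off peanut permanently, no if kept on 1/16 teaspoon.
- Per protocol (SAP 4): a child stopped at Visit 1 who attends no updosing visits is out; one who continues can qualify.
- Treatment-failure label (8.4): given only after failing 1/16 teaspoon. A child stopped at Visit 1 without that trial has no stated status. Week 72 for the endpoint challenge would follow from the general schedule but is spelled out only for the child who fails 1/16 teaspoon.

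**Step 5: the plan's own figure.** Inputs from Protocol 13.7: 55% vs 10%, drop-out 20%, drop-in 5%, 36 per group, 0.05 level, continuity-corrected chi-squared test; two-sided from 13.4.1.

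- Intervention: 0.55 × 0.80 + 0.10 × 0.20 = 0.46.
- Control: 0.10 × 0.95 + 0.55 × 0.05 = 0.1225. Difference d = 0.3375.
- Effective n after continuity correction: (36d − 1)² / (36d²) = 11.15² / 4.1006 = 30.3.
- Power at that n by the normal approximation: 84.2%. Exact enumeration of the corrected test: 85.9%.

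Both agree with the stated figure of approximately 85%.

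**Step 6: sensitivity to discontinuation.** The plan already allows 0.20 × 36 = 7.2 discontinuations. The other drop-out rates below are assumptions, not estimates of this conflict's effect.

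| Drop-out | Intervention rate | Power, approximate | Power, exact |
|---|---|---|---|
| 15% | 48.25% | 88.6% | 89.9% |
| 20% (plan) | 46% | 84.2% | 85.9% |
| 25% | 43.75% | 79.0% | 80.9% |
| 30% | 41.5% | 72.8% | 75.0% |

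Five points of drop-out is 0.05 × 36 = 1.8 children.

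**The case against.** The strongest reply is that the rules apply at different times. The entry condition and Visit 1 govern the first feeding. The 1/16 teaspoon provision governs later loss of tolerance, since 3.1.3 refers to symptoms during the study and 8.4 deals with unscheduled visits. This is a plausible reading, and it disposes of the middle row of the first table. But neither section states it. The 8.4 wording covers a child who is unable as well as one who becomes unable, and Visit 1 comes after randomization. Figure 2 is not shown in the text available here, and feeding details are deferred to the Manual of Procedures; either might settle the branch.

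On severe symptoms, the reply is that the severe-symptom rule is the more specific one, still leaves discontinuation, and sits among provisions that give the investigator discretion. That is largely right. A reader might infer a flat contradiction here, but the documents support only a tension over which provision governs.

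On consequences, this is a single-site trial, ITT membership is fixed, and the SAP runs the instrumental-variable analysis only if crossover is high. The SAP defines the per-protocol population but names no analysis that uses it, and it attaches no analysis to the treatment-failure label. All of this stands and limits the weight of the point.

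**Conclusion.** The conflict is real but narrow. It concerns failure of 1/8 teaspoon at the first or a repeated Visit 1, with a secondary tension for severe symptoms at that amount. It is an internal inconsistency worth correcting; no stated figure is wrong.

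Three stronger conclusions are tempting and are not supported:

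- That three sections give three different rules, or that any child who loses tolerance of 1/8 teaspoon is caught. There are two rules, and they agree for non-severe loss of tolerance after Visit 1.
- That the loss can be counted. The documents give neither the size of the 443 mg stratum nor a Visit 1 failure rate. The per-child figure of (0.55 − 0.10) / 36 = 1.25 points is probably an upper bound: it gives a child on 1/16 teaspoon the full 55% success rate. A child who also fails 1/16 teaspoon stops under both rules, and some stoppages fall within the 20% already allowed.
- That the primary analysis set or the power is undermined. Neither is.

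What depends on the rule applied is receipt of the intervention, the crossover count, per-protocol membership and any instrumental-variable estimate. With 36 children per arm, even one or two children could shift these counts noticeably.

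**What to change.** Reconcile the two statements in 3.1.3, the Visit 1 limit in 8.3, and the opening and severe-symptom provisions of 8.4 into one rule, chosen by the investigators and DSMB. It should:

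- cover failure of 1/8 teaspoon at a first or repeated Visit 1;
- cover severe symptoms at 1/8 teaspoon, where no reduction of two or more steps exists, and say which provision governs;
- state the child's status and the timing of the endpoint DBPCFC in each branch.

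State the rule once and cite it from 3.1.3, 8.3 and 8.4. Check that Figure 2 and the Manual of Procedures agree with it. Record on the eCRF which branch was applied, so that crossover and per-protocol status can be derived consistently.

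The cost is wording in three sections and one eCRF field, with no added visits or participants. This point takes no view on which rule is clinically right.

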### AADCRC

specifying the types and amounts of the commercial foods allowed for home ingestion. They also will be required to strictly avoid the food allergen other than the amount under the study. They will return every 8 weeks to attempt a supervised feeding of the next higher amount, as shown in **Figure 2**. If successfully consumed, they will continue the one step higher amount daily. When participants have exceeded 3/8 teaspoon of peanut butter, alternative forms (Bamba™, candies) can be substituted but such substitutions will be performed as observed feedings. (Table available in the MOP.) If subjects have symptoms at 1/8 teaspoon peanut butter during the study, they will be permitted to trial 1/16th teaspoon under observed feeding, but this will be the lowest amount allowed in the study.

# **3.1.4 Control Arm Procedures**

Children randomized to the control arm will follow standard care of strict avoidance of peanut. They will have a repeat DBPCFC to peanut at a time determined by a surveillance algorithm as described in Section 13.3, to match the distribution of DBPCFC to those of the intervention group. Based on the outcome of the DBPCFC, they will either be considered no longer allergic (naturally tolerant, NT) if they tolerate the full dose of the challenge (9043 mg) or will continue strict avoidance under clinical care off of the study.

